15 STATISTICAL METHODS AND CONSIDERATIONS

15.1 General Considerations

Prior to the analysis of the final study data, a detailed Statistical Analysis Plan (SAP) will be written, describing all analyses that will be performed. The SAP will contain any modifications to the analysis plan described below. All analyses will be performed using SAS® (SAS Institute, Inc., Cary, NC, USA) or R (R Foundation for Statistical Computing, Vienna, Austria).

For the purposes of analyses, baseline will be defined as Day 0 (Randomization/Visit 2). Except where otherwise noted, comparisons of continuous variables between treatment arms will utilize two-sample t-tests or multiple linear regression/ANOVA, proportions will be compared using Fisher's exact test, and rate ratios will be compared using Poisson regression. Except where otherwise noted, all tests will be two-sided and statistical significance will be determined at the 0.05 level. Missing data methods for the primary and key secondary endpoints will be described in the SAP. No adjustment for multiple comparisons will be made.

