15.9 Sample Size

The primary endpoint is the difference between treatment groups of the change in weight-for-age z-score from Visit 2 to Visit 4 (Week 24). Data from prior studies of similar populations and durations are available to estimate sample size and power for the study including a randomized, placebo-controlled trial of oral GSH in Italian children chronically taking pancreatic enzymes, as well as a factorial randomized trial comparing antipseudomonal regimens in US children with newly acquired *Pseudomonas aeruginosa* infection. These studies suggest a standard deviation of the change in weight-for-age z-score ranging from 0.20 to 0.29. A query of CF registry data of a similar population found the standard deviation of the 6-month change in weight-for-age z-score to be higher (0.37). A previous study of oral GSH in children, conducted in Italy, found the weight-for-age z-score difference between the GSH arm and the placebo arm after 6 months of therapy to be 0.34. The following table provides example weight changes in kilograms over a 6 month period for certain patient age and sex combinations, as well as how those gains translate into changes in weight-for-age z-score.

Subject Age and Sex at Baseline	Weight Baseline (kg)	Weight Visit 4 (kg)	6-month change (kg)	Weight at baseline (z-score)	Weight at Visit 4 (z-score)	6 month change (z-score)
9-year old boy	25	28	3	-0.87	-0.46	0.42
7-year old girl	19	20.75	1.75	-1.27	-1	0.27
3-year old boy	14	15.25	1.25	-0.21	0.01	0.22
4-year old girl	15	17.5	2.5	-0.4	0.28	0.68

The figure below displays a range of detectable treatment effect sizes and resulting sample sizes for 3 standard deviations (SD = 0.2, 0.3 and 0.4) Assuming a conservative standard deviation of 0.4, a total sample size of 54 provides 90% power to detect a treatment effect of 0.36 or greater. It is anticipated from prior CF trials conducted through the TDNCC that the attrition rate will be less than 10% for a study of this duration, thus it is reasonable to expect that a total sample size of 60 will enable at least 54 subjects to complete the trial.

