3.4 Primary Endpoint

Weight-for-age z-score, the primary outcome measure, will be calculated using CDC reference equations based on age, sex, and weight. The number and percent of expected and observed measurements of weight-for-age z-score across visits will be tabulated by treatment group, along with reasons for missingness and the number and percent of participants with both baseline and end of study measurement.

The primary endpoint is the difference between the GSH and placebo groups in the change in weight-for-age z-score from Visit 2 (Baseline) to Visit 4 (Week 24). The difference between treatment groups will be estimated using a linear mixed effects model which will incorporate Visit 3 (Week 12) weight-for-age z-score measurements. The model will adjust for randomization strata, i.e., sex (male, female), baseline age (< 6 years, ≥ 6 years), baseline weight-for-age z-score category (< -0.52, ≥ -0.52), and historical fecal elastase (<200 µg/g, ≥200 µg/g, unavailable) and assume, if estimable, an unstructured covariance structure. Least squares mean changes at each visit and the estimated treatment differences with corresponding 95% confidence intervals from the model will be presented. The model-based p-value for the Visit 4 (Week 24) treatment difference will be evaluated against a two-sided 0.05 level of significance. Graphical displays will be used to show unadjusted mean changes in weight-for-age z-score across visits for the two treatment groups.

Sensitivity analyses of the primary endpoint will include:

- Performing the primary efficacy analysis on the per-protocol population.
- Performing the primary efficacy analysis on the sub population of subjects determined to be pancreatic insufficient (defined as fecal elastase < 200 µg/g).
- Least favorable treatment group imputation, which imputes missing values with the mean change from the treatment group with the worst change in the observed case analysis,

conservatively assuming that any participants who dropped out of the study had a less than favorable result.

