Model-based mean changes in weight-for-age z-score from baseline to Visit 4 and treatment differences with corresponding 95% confidence intervals and p-values from the sensitivity analyses will be tabulated. The treatment difference for 24-week change in weight-for-age z-score and corresponding 95% confidence intervals based on the primary efficacy analysis as well as those from the sensitivity analyses will be graphical represented.

Subgroup analyses defined by baseline covariates will be performed, as subgroup size allows, using linear mixed models incorporating Visit 3 measurements without additional adjustment for randomization strata. Subgroups are as follows:

- Age (2-6 years, 6-10 years)
- Sex (Male, Female)
- CF Genotype (F508 del Homozygous, F508 Heterozygous, Other)
- Height Percentile (< 50th Percentile, ≥ 50th Percentile)
- Weight Percentile (< 30th Percentile, ≥ 30th Percentile)
- FEV₁ percent of predicted (< 90%, ≥90%)
- Fecal Elastase (< 100 µg/g, ≥ 100 µg/g)
- CFTR Modulator Use (Yes, No)
- Use of Appetite Stimulants (Yes, No)
- Use of Nutritional Supplements (Yes, No)
- G-tube (Yes, No)

Model-based mean changes in weight-for-age z-score from baseline to Visit 4 and treatment differences with corresponding 95% confidence intervals and p-values from the subgroup analyses will be shown. The treatment difference for Visit 4 weight-for-age z-score and corresponding 95% confidence intervals based on the subgroup analyses will be graphically represented.

Summary statistics will be tabulated by treatment group for weight-for-age z-score at baseline, Week 12, and Week 24. Both absolute and relative changes from baseline will be presented for Week 12 and Week 24. Treatment differences and corresponding 95% confidence intervals will be provided for the Week 24 absolute and relative changes. Figures displaying mean values and mean changes from baseline by treatment group across visits will be provided for each anthropometric endpoint.

Individual weight-for-age z-scores trajectories will be plotted across study visits by treatment group.

The corresponding descriptive summaries are outlined in Appendix A, Section A.4.

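### SAP 3.4 plans p-values within up to 23 subgroup levels and states no interaction test, so a uniform treatment effect will often look uneven

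*SAP*

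**What the plan says.** After the primary model and its sensitivity analyses, SAP 3.4 adds subgroup analyses by baseline covariates, to be done where subgroup size permits. No minimum size is given. They are fitted "using linear mixed models incorporating Visit 3 measurements without additional adjustment for randomization strata". Eleven factors are listed: age, sex, genotype, height percentile, weight percentile, FEV₁ % predicted, fecal elastase, CFTR modulator use, appetite stimulants, nutritional supplements and G-tube. Genotype has three levels and the others have two, so there are at most 10 × 2 + 3 = 23 levels.

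On reporting, the SAP says that "treatment differences with corresponding 95% confidence intervals and p-values from the subgroup analyses will be shown". A figure of differences with 95% confidence intervals is also planned. No interaction or heterogeneity test is mentioned there or elsewhere in the supplied protocol and SAP, and the set is not labelled exploratory.

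Protocol 15.1 sets the default: "all tests will be two-sided and statistical significance will be determined at the 0.05 level", and "No adjustment for multiple comparisons will be made". Protocol 15.3 does not plan this list. It has only the pancreatic-insufficient subpopulation, as a sensitivity analysis.

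The age subgroup is written "Age (2-6 years, 6-10 years", while the randomization strata in the same SAP section use "baseline age (< 6 years, ≥ 6 years".

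**The concern.** Readers use a subgroup table to judge whether the effect differs between kinds of children. A p-value inside each level answers another question: whether that level alone, with its smaller sample, excludes zero. If one level crosses 0.05 and the other does not, the table looks like evidence of a differential effect, yet the two estimates may be fully compatible.

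The trial is sized for one comparison in about 54 children. Cutting it in two lowers power in each half to a range where significant and non-significant results are almost equally likely under the planned effect. With 11 factors, a display of this kind is likely to contain several such contrasts. They could be misread as showing which children benefit.

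**Working it through.** **Inputs.** From Protocol 15.9: "a total sample size of 54 provides 90% power to detect a treatment effect of 0.36 or greater" and "Assuming a conservative standard deviation of 0.4". From Protocol 15.1: two-sided 0.05 and no multiplicity adjustment. From Protocol 8.1: equal allocation. The documents give no subgroup prevalences, so 50:50 is an assumption, with 70:30, 80:20 and 90:10 as the range. The calculations use t-tests on the 24-week change, not the mixed model, with arms balanced within levels for the closed-form results.

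**1. The plan's own figure.** With 27 per arm, the noncentrality is 0.36 / (0.4 × √(2/27)) = 3.31 on 52 degrees of freedom. Power is 90.06%, so the stated 90% is reproduced.

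**2. Power within a level.** A 50:50 split leaves 27 children, or 13.5 per arm. The noncentrality is 0.36 / (0.4 × √(2/13.5)) = 2.34 on 25 degrees of freedom, and power is 61% (59.6% at 13 per arm, 63.0% at 14). With 20, 14 and 10 children in a level, power is 48%, 34% and 24%.

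**3. Discordant levels under a uniform effect of 0.36.** The two levels contain different children, so P(exactly one significant) = p₁(1 − p₂) + p₂(1 − p₁).

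| Split | Power, larger level | Power, smaller level | P(one significant, one not) |
|---|---|---|---|
| 50:50 | 61.3% | 61.3% | 2 × 0.613 × 0.387 = 47% |
| 70:30 | 76.8% | 39.3% | 56% |
| 80:20 | 82.3% | 26.2% | 65% |
| 90:10 | 86.7% | 12.2% | 78% |

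Over ten 50:50 factors the expected number of discordant pairs is 10 × 0.474 = 4.7.

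**4. All 11 factors together.** Simulation with 54 children, SD 0.4, mutually independent factors and 2,000 runs per scenario, once with 50:50 binary splits and once with a mix of uneven splits:

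| True effect in every child | Mean discordant factors of 11 | P(at least one discordant) |
|---|---|---|
| 0.36 | 5.5 to 6.2 | 93% to 98% |
| 0.18 | 3.6 to 3.7 | 78% to 79% |

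**5. No effect anywhere.** Expected false positives are 23 × 0.05 = 1.15. If the 23 tests were independent, P(at least one) would be 1 − 0.95²³ = 69%. They re-cut the same children, and the simulation gives 49% to 50%.

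**6. What an interaction test would do.** Each factor gives a false signal 5% of the time. Across 11 factors, P(at least one) = 1 − 0.95¹¹ = 43% (simulated 41% to 45%). For a 50:50 factor the standard error of the difference between level effects is √(4 × 0.4² / 13.5) = 0.218. Power for a 0.36 difference in effect is Φ(0.36/0.218 − 1.96) = 38%. For 80% power the difference must be (1.96 + 0.84) × 0.218 = 0.61.

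**The case against.** Much can be said for the plan. No decision rests on the subgroups, and SAP 3.4 ties its 0.05 test to the Visit 4 primary difference. Estimates with confidence intervals by level are legitimate, and the planned figure mentions no p-values. Twenty-three is a ceiling, because small levels may not be analysed. Not all factors can use 54 children either: FEV₁ exists only for those aged 4 or older who can perform spirometry reproducibly. The SAP does not say outright that separate models are fitted. One model per factor would also fit its wording, and Appendix A.4, which outlines the outputs, is not in the supplied text. All of this stands. But the sentence attaches the p-values to treatment differences, and no interaction test is stated.

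The remedy also has limits. Like for like under no effect, about 43% of trials would have at least one false interaction flag, against about 49% with at least one significant level. The gain lies in the per-factor rate under a uniform effect: 5% instead of about 47%.

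Two stronger readings are tempting and do not hold. A reader might infer that leaving out the randomization strata produces the chance splits. It does not: omission alone does not push within-level tests above 5%. It costs some precision and comparability with the primary model. It is partly defensible in small levels, and some strata are redundant, since sex is constant within its own subgroup and the 30th-percentile weight split is the −0.52 stratum (Protocol 8.1). A reader might also take the age bands as a real mismatch with the strata. In a trial of children aged at least 2 and under 11, 6-10 in completed years is the ≥6 stratum, and 2-6 reads as shorthand for under 6. The label is ambiguous, which is an editorial matter.

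**Conclusion.** The point holds as a weakness in planned subgroup reporting. Up to 23 within-level p-values are planned with no stated test of whether effects differ. Under the design effect of 0.36, identical in all children, a two-level factor looks discordant 47% of the time at 50:50 and up to 78% at 90:10. With no effect, about half of trials show at least one significant level.

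These figures rest on assumed prevalences, independent factors, all levels being analysed (for the trial-wide figures) and t-tests on change scores. The per-factor result does not depend on independence between factors and persists over the whole prevalence range. It does depend on the true effect: at 0.18, about 3.6 of 11 factors are discordant rather than 5.5 to 6.2. It would be wrong to infer that the primary result is compromised. The primary analysis is unaffected.

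**What to change.** For each factor, fit one mixed model in all m-ITT subjects with that factor available. Include treatment-by-visit-by-subgroup terms and the primary model's randomization strata, leaving out a stratum that duplicates the factor. The strata are kept for precision and comparability with the primary model.

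Report the Week 24 interaction p-value, and the effect with 95% confidence interval in each level, without within-level p-values. Label the set exploratory and state the number of interaction tests. Write the age groups as <6 and ≥6 years.

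The cost is SAP wording and a small change to the subgroup program. No visit, procedure or sample size changes. The downside is low interaction power, so most tests will be inconclusive and moderate true differences will be missed. An isolated interaction p-value below 0.05 should be read against the roughly 43% chance of at least one among 11.

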6.2 Inclusion Criteria

Inclusion Criteria:

1. Male or female ≥ 2 and < 11 years of age at Visit 1
2. Documentation of a CF diagnosis as evidenced by one or more clinical features consistent with the CF phenotype and one or more of the following criteria:
 - Sweat chloride ≥ 60 mEq/liter by quantitative pilocarpine iontophoresis test (QPIT)
 - Two well-characterized mutations in the cystic fibrosis transmembrane conductance regulator (CFTR) gene
3. Weight-for-age between the 10th and 50th percentiles at Screening (Visit 1) (using the Center for Disease Control (CDC) reference equations)
4. Current chronic use, greater than 8 weeks before Day 0, of pancreatic enzyme replacement therapy (PERT) for management of pancreatic insufficiency
5. Written informed consent (and assent when applicable) obtained from subject or subject's legal representative and ability to comply with the requirements of the study
6. Clinically stable with no significant changes in health status within 2 weeks prior to Day 0

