15.4 Analysis of Secondary Endpoints

Descriptive analyses and graphical displays will be used to summarize all secondary endpoints. Endpoints will be compared between the GSH and placebo treatment groups from Visit 2 through Visit 4.

Continuous secondary endpoints which are collected at Visits 2, 3, and 4, including absolute changes and relative changes in weight, weight percentile, height, height-for-age z-score, height percentile, BMI, lung function (FEV₁ (liters and % predicted), FVC (liters and % predicted) and FEF₂₅₋₇₅ (liters/second and % predicted)), and fecal calprotectin, will be modeled using a linear mixed effects model similarly to the primary endpoint. The estimated treatment effect for the change for each secondary endpoint from Visit 2 to Visit 4 will be presented as well as corresponding 95% confidence intervals and p-values. Predicted values for spirometry measures at each visit will be calculated for those subjects ≥ 4 years of age at baseline using the Global Lung Initiative reference equations [33] Height for age z-score and height and weight percentiles will be calculated using the CDC reference equations [32].

Continuous measures collected only at Visit 2 and Visit 4, including neutrophil, platelets, and hs-CRP will be analyzed using ANOVA. The estimated treatment effect for the change for each secondary endpoint from Visit 2 to Visit 4 will be presented as well as corresponding 95% confidence intervals and p-values.

Event rates for hospitalization, PEs, intravenous antibiotic usage, inhaled antibiotic usage, and oral antibiotic usage from Visit 2 through Visit 4 will be descriptively summarized and differences in the proportions of subjects with an event between the treatment groups will be estimated with accompanying 95% confidence intervals. Event rates will be compared between treatment groups using Poisson regression.

Descriptive analyses will be used to summarize GI parent questionnaire data collected throughout the study. For each of the 14 gastrointestinal symptoms measured, changes from Visit 2 to Visit 4 will be summarized and compared between the GSH and placebo treatment groups.

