3.8 Anthropometric Endpoints

In addition to the primary endpoint of weight-for-age z-score, the following anthropometric endpoints will be summarized: weight (kg), weight-for-age percentile, Body Mass Index (BMI, kg/m²), BMI-for-age z-score, BMI-for-age percentile, height (cm), height-for-age z-score, and height-for-age percentile. Height-for-age z-score, BMI percentile and z-score, and height and weight percentiles will be calculated using CDC reference equations.

For each of these endpoints, a linear mixed effects model analogous to the primary endpoint model will be used. Least squares mean changes at Week 24 and the estimated treatment differences with corresponding 95% confidence intervals and p-values will be presented.

In addition to the model based estimates, summary statistics will be tabulated by treatment group for each endpoint at baseline, Week 12, and Week 24. Both absolute and relative changes from baseline will be presented for Week 12 and Week 24. Treatment differences, corresponding 95% confidence intervals, and p-values will be provided for the Week 24 absolute and relative changes. Figures displaying mean values and mean changes from baseline by treatment group across visits will be provided for each anthropometric endpoint.

The corresponding summaries and analyses are outlined in Appendix A, Section A.8.

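### Relative change of z-scores (SAP 3.4 and 3.8) has no stable meaning: under the usual formula a gain from a negative baseline is reported as a negative percentage. A minor item confined to supportive and secondary outputs.

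*SAP*

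**What the plan says.** SAP 3.4 tabulates summary statistics for weight-for-age z-score at baseline, Week 12 and Week 24, with absolute and relative changes, and then states: "Treatment differences and corresponding 95% confidence intervals will be provided for the Week 24 absolute and relative changes". No p-value is planned for that summary.

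SAP 3.8 lists eight further anthropometric endpoints, including BMI-for-age and height-for-age z-scores. Alongside the mixed model it states: "Treatment differences, corresponding 95% confidence intervals, and p-values will be provided for the Week 24 absolute and relative changes".

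Protocol 15.4 gives the list of secondary variables for the mixed model in these words: "including absolute changes and relative changes in weight, weight percentile, height, height-for-age z-score, height percentile, BMI". Relative change in height-for-age z-score is therefore also in the protocol's analysis section. Protocol 5.2, which lists the endpoints, names relative change for spirometry only.

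Protocol 6.2 limits entry to weight-for-age from the 10th to the 50th CDC percentile at screening. No entry limit is set for height or BMI.

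The supplied text does not define relative change or say how a negative or near-zero baseline is handled. Appendix A, Sections A.4 and A.8, which outline these outputs, is not in the supplied text.

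**The concern.** The zero of a z-score is the reference median, not an absence of weight or height, so a percentage of a z-score has no fixed meaning. In this trial the entry rule makes nearly every weight z denominator negative and lets the range end at zero, where the ratio is undefined.

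Two things follow under change divided by baseline. A child who gains scores a negative percentage, so an effective treatment would usually show a negative relative difference next to a positive absolute difference for the same variable. And the size of the percentage depends mainly on how close to zero the child started.

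Height and BMI z-scores can take either sign, so there the direction of a gain also varies from child to child. Those are the variables for which SAP 3.8 adds p-values.

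**Working it through.** **The plan's own figure.** Protocol 15.9: "Assuming a conservative standard deviation of 0.4, a total sample size of 54 provides 90% power" for an effect of 0.36. With a two-sided 0.05 level and equal allocation, 27 per arm gives 90.1% power by the noncentral t distribution, so 54 is reproduced. That calculation uses absolute change.

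**Sign, from the protocol's example table (15.9).** Relative change = 100 × (Visit 4 z − baseline z) / baseline z.

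- 9-year-old boy: (-0.46 + 0.87) / -0.87 = -47%
- 7-year-old girl: (-1 + 1.27) / -1.27 = -21%
- 3-year-old boy: (0.01 + 0.21) / -0.21 = -105%
- 4-year-old girl: (0.28 + 0.40) / -0.40 = -170%

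All four gain. The 3-year-old has the smallest gain (0.22) but about five times the percentage of the 7-year-old (gain 0.27), because he starts nearer zero.

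**Dependence on the starting point.** The same gain of 0.36 reads 0.36/-1.28 = -28%, 0.36/-0.52 = -69%, 0.36/-0.25 = -144% and 0.36/-0.10 = -360%.

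**Weight z at trial level.** Simulation of 20,000 trials per scenario, 27 per arm, comparing mean individual relative change with a two-sample t interval.

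- From the documents: effect 0.36, SD 0.4, entry range -1.28 to 0.
- Assumed: placebo change 0.05 to 0.10 (0.10 is the placebo change in the earlier Italian trial, Protocol 1.2); baselines uniform in z or in percentile up to the stated limit; change independent of baseline.

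| Highest baseline z | Relative difference negative | Interval wholly below 0 | Median width (points) |
|---|---|---|---|
| 0 (whole entry range) | 85–87% | about 23–26% | about 440–600 |
| -0.05 | about 98% | 54–58% | 176–207 |
| -0.10 | about 99% | 65–69% | 127–145 |
| -0.25 | over 99% | 80–82% | 79–87 |

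The absolute-change interval shows the benefit in 90% of the same trials. A uniform spread puts 7.8% (z) to 10.0% (percentile) of 54 children, about 4 to 5, within 0.10 of zero.

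Protocol 15.9 also reports smaller SDs: "These studies suggest a standard deviation of the change in weight-for-age z-score ranging from 0.20 to 0.29". With those, the median width is still about 310–500 points over the whole range. It is 45–66 points if baselines stop at -0.25, and the interval is then wholly below zero in 96–100%.

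**Dividing by the absolute value of baseline.** With all baselines negative this is the mirror image: same widths, sign restored. At SD 0.4 the interval excludes zero in about a quarter of trials over the whole range, and in about 80% if baselines stop at -0.25.

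**BMI z.** From Protocol 1.2: mean baseline (-0.76 - 0.57)/2 = -0.665, placebo change 0.22, effect 0.60 - 0.22 = 0.38. Assumed: baseline SD 0.5–1.0, change SD 0.4–0.5. The relative-change interval excludes zero in about 3–10% of trials, against 78–93% for absolute change.

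**Height z.** The documents give no inputs, so no figure is offered.

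**The case against.** The strongest reply is that little depends on these outputs. The SAP 3.4 sentence belongs to a table of summary statistics with no p-value, SAP 3.8 puts the mixed model first, and the absolute difference is promised in the same sentence. That stands, and it makes this a minor item. A reader might infer that the primary result or the power is compromised. The documents do not support that: the primary model, its p-value and the sample size all rest on absolute change.

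Second, the formula is assumed, and Appendix A may define another. This also stands, so the sign reversal is conditional on change divided by baseline. It cannot be said that the plan lacks a definition, only that the supplied text has none. Using the absolute value of baseline would remove the sign problem but not the instability near zero.

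Third, a reader might infer that an interval hundreds of points wide is to be expected. The documents give no baseline distribution, and none of the four example children starts within 0.10 of zero. The great width needs children very close to zero; without them the interval narrows. Under change divided by baseline, however, it narrows around the wrong sign.

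Fourth, percentiles share part of the problem. A gain of 0.36 z raises the percentile by 28% from z = 0 (50.0 to 64.1), 78% from z = -1.28 (10.0 to 17.9) and 122% from z = -2 (2.3 to 5.1). This stands as a limitation. Percentiles are always positive, though, so a gain remains a gain.

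**Conclusion.** The concern holds as a minor one. The plan calls for treatment differences on relative change in three z-scores, with p-values for two of them. Under the usual formula these outputs would mislead: a true benefit of 0.36 in weight z would carry a negative relative difference in about 85–87% of trials with baselines over the whole entry range, and in nearly all trials if baselines stay below -0.25.

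The sign result rests on the assumed formula and on the entry rule, and it is visible in the protocol's own table. The widths also rest on assumed baseline distributions. The entry rule applies to the screening weight; a Visit 2 baseline that has drifted above zero would make the sign inconsistent rather than uniformly reversed. The BMI contrast rests on another trial's means and on assumed SDs.

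Only the supportive outputs of SAP 3.4 and the secondary outputs of SAP 3.8 are affected.

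**What to change.** Before unblinding, delete from SAP 3.4 and 3.8 the relative-change summaries, treatment differences, confidence intervals and (3.8) p-values for the weight-, height- and BMI-for-age z-scores, and report absolute change only. Carry this into any matching rows of Appendix A, Sections A.4 and A.8. State in the SAP that this replaces the relative change in height-for-age z-score listed in Protocol 15.4; Protocol 15.1 lets the SAP carry such modifications, so no protocol amendment is needed.

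Leave relative change as planned for kg, cm, kg/m² and spirometry. It may also stay for percentiles, with a note that absolute percentile change is to be read first because the relative figure depends strongly on the starting point.

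The cost is a short SAP edit and a few dropped table rows. No new data or analysis is required, and no endpoint named in Protocol 5.2 is lost.
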